The date of registering with a general practice in a different CCG (i.e. going from one in NEHF to outside of NEHF, or vice versa) may also have occurred up to a month earlier. However, hospital activity will be recorded throughout and it is unlikely that the dates of moving are other than random and therefore introduce bias between the intervention and control groups.

Pre-period

Baseline variables will be assembled using data recorded during the 'pre-period', which is the period before a patient's index date.

For comorbidities, data at patient level for three years prior to the index date will be used, consistent with, for example, the Patients At Risk of Readmission (PARR) predictive model.²⁶ A three-year lookback period will allow for more patients with a prior hospital admission to be identified than a shorter lookback period.²⁷ The number of new patients identified through prior hospital admissions progressively diminishes over increasing lookback periods.²⁷ A longer lookback period also allows for more comorbidities to be identified.^{27,28} Most studies that explore varying lookback periods do not go beyond one year;²⁸ however, one study investigated up to five years' lookback.⁽²⁸⁾ A comparison of model fit and predictive ability for both modelling deaths and readmissions within 30 days found that both improved over the length of the lookback period, with a five-year lookback period being better than a three-year lookback period.²⁸ However, the magnitude of improvement progressively diminished over increasing lookback periods,^{28,29} with an increase in comorbidity prevalence of less than 1% when including admissions up to three years compared with two.²⁹ As some comorbidities may resolve over time, a three-year

lookback should adequately balance the need to identify patient characteristics while not unduly identifying historic comorbidities that have since been resolved.

Note that some patients may have received interventions other than ICTs before the index date, which may affect some of the prior hospital activity covariates. However, it is assumed that any use of these services would not be unbalanced between the groups, after matching, and any risk of an imbalance is outweighed by the benefits of including information on hospital activity just before patients were referred to ICTs in the matching process and regression model.

Baseline variables

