Appropriate baseline variables will be included in both the matching and the regression models. All baseline variables are calculated on pre-period data. Potential baseline variables to include in the matching or as covariates in the modelling are listed in Table 3.

Table 3. Potential baseline variables

Category	Variables at patient level
Demographics & socio-demographics	
 • Approximate age at index date • Gender • Ethnicity • Average socioeconomic deprivation deciles, based on the Index of Multiple Deprivation (IMD) 2015, available at layer super output area (LSOA) level • Urban/rural classification at lower LSOA level, based on the 2011 census
Prior hospital use	
 • Number of emergency admissions in the last 60 days of the pre-period • Number of emergency admissions in year -1, the last year of the pre-period (i.e. 365 to 1 day before index date) • Number of emergency admissions in year -2 of the pre-period (i.e. 730 to 366 days before index date) • Number of ACS emergency admissions in the last 60 days of the pre-period • Number of ACS emergency admissions in year -1 of the pre-period • Number of ACS admissions in the year -2 of the pre-period • Number of elective admissions in year -1 of the pre-period • Number of A&E attendances in year -1 of the pre-period • Number of outpatient attendances in year -1 of the pre-period • Number of missed outpatient visits in year -1 of the pre-period • Average length of stay in year -1 of the pre-period
Health variables	
 • Elixhauser list of comorbidities, identified in the pre-period • Specific comorbidities linked to frailty, identified in the pre-period³⁰ • Other comorbidities predictive of hospital emergency admission, as identified in the Inpatient Outpatient A&E and GP(IPOPAEGP) model,³¹ identified in the pre-period

	
 • Number of Elixhauser comorbidities in the pre-period • Number of frailty comorbidities in the pre-period
Support	
 • Resident in a nursing or residential home
Time period	
 • Index date/period (quarter & year, e.g. q1y1, q2y1...)
Level of care available	
 • Locality in which the patient is registered with a GP

All comorbidities will be defined using data from any diagnosis field in any hospital admission in the pre-period.

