The IPOPAEGP model³¹ is a risk prediction model of hospital admissions that builds on and improves on earlier models such as the PARR algorithm and identifies a number of comorbidities predictive of hospital admission.²⁶ Those included in the IPOPAEGP algorithm that are not already captured within the Elixhauser or frailty lists and can be identified from inpatient data include myocardial infarction, cerebrovascular disease, connective tissue disease and mental ill health, such as miscellaneous cognitive dysfunctions. The risk prediction model also identifies number of outpatient visits missed in the first year of the pre-period. This variable is also included in our list of potential covariates as the number of missed appointments may be correlated with how amenable a patient is to health care interventions, which may be a confounder.³⁶

Although some of the comorbidities can be cured, it is assumed that any issues reported in the pre-period will be relevant to the overall health or frailty of the person and therefore can be included as a potential covariate.

There is some overlap between the definitions of the health condition: 'depression' (Elixhauser list) and 'anxiety or depression' (frailty list).

It may not be possible to get balanced groups on all listed potential comorbidities. The IAU will empirically determine which covariates are most predictive of emergency admissions and optimise balance between the groups based on order of priority (see section on Choice of matching variables, p. 28). Although the IAU expects to adjust for all potential covariates in the regression models, the same priorities will apply to the regression models if not all comorbidities can be adjusted, for example due to correlation between variables.

NEHF CSU is considering including whether a person is a care home resident as a criterion for selection to ICTs. Residents in nursing or residential care homes have different hospital activity than people living at home.³⁷ Furthermore, people who are socially isolated are often at higher risk of admissions.³¹ Therefore information on whether patients were residents in nursing and residential homes at their index date will be included as a covariate.

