The IAU will match on patient characteristics, to ensure a similar patient case-mix between the groups. Although the IAU will ultimately assess balance across all variables detailed in the section on Baseline variables (p. 25), we are likely to only include a subset of those variables in the matching algorithm. The IAU will empirically explore which covariates are most predictive of emergency admissions among the potential control group and whether the conditions are prevalent in the intervention and control groups. The subset of variables included in the matching algorithm will be adapted to optimise balance between the two groups on those variables considered most strongly predictive of the outcome, for instance the prior numbers of emergency admissions, but will also aim to optimise balance across the wider set of variables.

Matching parameters

Table 5 gives the matching algorithm parameters to be used for this analysis.

Table 5. Matching parameters

Parameter	Value
Estimand	ATT
Number of controls per intervention patient	1
Control sampling method	Without replacement
Population size	2,000
Maximum generation	1,000

Number of generations to wait	100
-------------------------------	-----

ATT=average treatment effect for the treated

Diagnosics

Balance will be assessed across all baseline variables listed in the section on Baseline variables (p. 25), even though not all variables will be included in the matching algorithm.

Balance will be assessed using the standardised difference, which is defined as the difference in means as a proportion of the pooled standard deviation.⁴⁰ Although the standardised difference should ideally be minimised without limit, a standardised difference below 10% has been used to describe negligible imbalance.⁴¹ The standardised difference is a better measure of balance than formal statistical tests, as the latter depend on the size of the groups, as well as on the level of similarity.⁴² The distribution for continuous or count variables will also be assessed.

Statistical analysis

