- 1.0 a table for showing study length and reasons for censoring (leaving the study).

Data cleaning and validation checks

Data cleaning and data validation checks will be performed by the IAU Data Management team, in accordance with the IAU Data Management Quality Assurance Process. Where appropriate, a summary of the results can be produced for the technical appendix.

Data flow diagrams

The following diagrams will be produced for the technical appendix:

- 1.0 data linkage process diagram
- 2.0 data flow diagram of study cohort selection.

5. Addendum

This section has been added to the original statistical analysis protocol (SAP) document to provide further clarifications and information on modifications to the original SAP. The original SAP was agreed in September 2017 with this section added in July 2018.

Definition of study cohort, page 18

In addition to the exclusion criteria described on page 18 of this document, the following exclusion criteria were applied prior to the analysis:

- Patients with no valid Lower Layer Super Output Area (LSOA) geographic area – this variable was used to determine a patient’s level of socioeconomic deprivation
- For potential control patients, patients more than 2 years’ older than the oldest ICT patient or more than 2 years’ younger than the youngest ICT patient – this was to limit the size of the dataset of potential controls in the matching process

Study endpoints, page 21

Here we provide further clarification on how variables were defined.

Elective admissions are defined as those that are ‘ordinary’ or day cases and exclude maternity and regular day/night cases.

When calculating readmission rates, the NHS Outcomes Framework guidance⁵⁶ was followed, with the exception of also including elective day cases as potential offsets for the calculations. This was consistent with the definition of elective admissions described above, which includes both ‘ordinary’ and day cases.

For the variable average length of stay in the year prior to the index date, any hospital spell that starts in the pre-period but continues into the follow-up period was included in its entirety within the pre-period. For the outcome measure average length of stay in the follow-up period, we only included spells that both start and finish within the follow-up period. There is no expected bias between the ICT and matched control groups, as both had access to the same hospitals.

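### Baseline average length of stay counts nights after the index date, and the stay in progress at referral is dropped from the length-of-stay outcome; access to the same hospitals does not show that this is free of bias

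*Protocol*

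**What the plan says.** The Baseline variables section of the Protocol states the rule: "All baseline variables are calculated on pre-period data". The Pre-period section defines that period as the time before the index date, and Table 3 spells out year -1 as ending the day before it. Table 3 lists "Average length of stay in year -1 of the pre-period" among the candidates for matching and adjustment.

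The Addendum (Study endpoints) records how the variable was built: "any hospital spell that starts in the pre-period but continues into the follow-up period was included in its entirety within the pre-period". For the follow-up outcome, "we only included spells that both start and finish within the follow-up period". It then concludes: "There is no expected bias between the ICT and matched control groups, as both had access to the same hospitals".

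On use of the variable, the Baseline variables section says "Although the IAU expects to adjust for all potential covariates in the regression models", with a reservation if not all can be included. The section on choice of matching variables says "we are likely to only include a subset of those variables in the matching algorithm". Balance is assessed on every listed baseline variable, whether or not it enters matching.

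**The concern.** A covariate measured partly after exposure begins can carry the effect of the exposure. Two things could go wrong here.

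- The intended impacts of the ICTs include fewer hospital bed days and fewer delayed transfers of care. If an ICT helps a current inpatient go home sooner, the saving appears as a shorter baseline stay and not as an outcome.
- If more ICT patients than controls are in hospital on the index date, future nights lengthen the ICT group's baseline stay. Adjustment then expects longer follow-up stays in that group and credits the ICT with the gap.

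The index date is set differently in the two groups. For ICT patients it is the first referral, a clinical event; the Integrated care teams section names one referral from a hospital Medically Fit for Discharge list. For controls it is a registration-extract date, monthly, or quarterly for those under 65 (Addendum). Nothing in this makes the chance of being an inpatient on that date equal.

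**Working it through.** The Protocol gives no figure on this point, so there is none to reproduce. The check has two parts.

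**1. The definitions in symbols.** Take a patient with n completed spells totalling S nights in year -1, and a spell in progress at the index date with A nights elapsed and R nights remaining.

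- Baseline from pre-index nights only: (S + A)/(n + 1).
- Baseline as the Addendum builds it: (S + A + R)/(n + 1).
- Difference: R/(n + 1), made up entirely of post-index nights.
- Follow-up average length of stay: contains no part of A or R, because the spell did not start in follow-up.

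If the ICT shortens R by a fraction k, the baseline variable falls by kR/(n + 1) and the outcome does not move. This follows from the text without any assumption.

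**2. Size, by illustration.** All inputs here are assumptions, not document figures: 1,000,000 patients per group; log-scale severity SD 0.6 around 5 nights, so mean stay 5 × exp(0.6²/2) = 5.99 nights; 1 + Poisson(1) prior spells; exponential elapsed and remaining stays; in-hospital status independent of severity; linear adjustment for baseline length of stay alone; no true effect on later stays.

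Hand check of the baseline inflation: the mean of 1/(n + 1) with n = 1 + Poisson(1) is exp(-1) = 0.368. With 10% in hospital and k = 0, the inflation is 0.10 × 5.99 × 0.368 = 0.220 nights, which matches the simulated 0.220.

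The shift is the adjusted ICT-minus-control difference using the Addendum's covariate, minus the same difference using the covariate cut at the index date.

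| In hospital at index, ICT / control | k | Shift (nights) | Share of 6 nights |
|---|---|---|---|
| 1.2% / 1.2% | 0.2 | +0.002 | 0.03% |
| 5% / 5% | 0.2 | +0.008 | 0.1% |
| 10% / 10% | 0.2 | +0.015 | 0.25% |
| 5% / 1% | 0.2 | -0.022 | 0.4% |
| 10% / 1% | 0.2 | -0.050 | 0.8% |
| 20% / 1% | 0.2 | -0.109 | 1.8% |
| 10% / 1% | 0 | -0.065 | 1.1% |

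With equal shares, the shift hides ICT benefit. With more ICT patients in hospital, it favours the ICT. In the last row an apparent benefit arises although the ICT does nothing.

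The only related document figure is 1 of 84 referrals in January 2017 from the discharge list (1/84 = 1.2%). That is a source of referral, not the share in hospital at index.

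**The case against.** The strongest reply is that the effect is confined to patients in hospital on the index date and is small. That stands: the shift in the table is at most about 2% of mean stay.

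Three further points have weight.

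- Table 3 lists potential variables, only a subset was likely to be matched on, and the Addendum's core adjustment list refers to prior-year hospital use without naming length of stay.
- Emergency admissions in the last two months are a core covariate, and controls have many candidate index dates. Both would partly even out the chance of being in hospital at index, though a recent admission is not the same as being an inpatient on the day.
- The control pool was about 750,000 records and forced reduced matching settings, so rematching is not trivial.

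A reader might infer more than the documents support:

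- **That ICT patients were matched to the wrong controls.** Use of length of stay in the final matching is not confirmed.
- **That adjustment removes the ICT effect.** Removal applies to the stay in progress at referral; admissions that start and finish in follow-up still count in the outcome.
- **That many future nights are involved.** Lognormal stays with mean 8 and log-SD 1.2 give 8 × exp(1.2²) = 33.8 nights for a stay in progress, half of it (16.9) after a random date. With log-SD 0.8 these become 15.2 and 7.6. The Protocol gives no stay distribution, the half-split does not suit referral dates (a patient on a discharge list is near the end of the stay), and nights added to a covariate are not bias in the estimate.
- **That post-index nights were left out of emergency bed days.** The whole-spell rule is stated only for average length of stay. Bed days are calculated over follow-up as unique days in hospital.

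**Conclusion.** The point stands as a contradiction in the Protocol and an unsupported claim of no bias. Post-index nights enter a variable declared to be pre-index, and this describes the analysis as carried out. Shared hospitals remove differences between hospitals; they do not equalise the chance of being an inpatient on the index date.

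For a stay in progress at referral, any ICT effect is certainly lost from average length of stay, a primary outcome. Where the covariate is in the model, it also receives that effect. The Protocol expects such adjustment but does not confirm it model by model.

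The resulting shift is probably small and its sign is unknown: +0.002 to -0.109 nights on about 6 in the illustration. That range rests wholly on assumed shares, stay lengths and a single-covariate linear model. It is not an estimate for this study, and the share in hospital at index is needed to narrow it.

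**What to change.** 1. Rebuild baseline average length of stay from pre-index information only, using either nights up to the day before the index date or spells completed before it. Either is defensible; state which.
2. Report the number in hospital on the index date by group, and adjust for that indicator.
3. Rerun the balance checks and the models that use the variable. Rematch only if length of stay was a matching variable.
4. Add a sensitivity analysis excluding patients in hospital at index.
5. Confirm that post-index nights of crossing spells are counted in emergency bed days, and say in the report that average length of stay does not capture effects on a stay in progress at referral.
6. Remove or qualify the statement that no bias is expected.

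The data are already held. The cost is recoding one covariate, adding one indicator and a rerun, as was already done for outpatient use after a data error. Rematching, if needed, is the heavier part given the size of the control pool.

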The Elixhauser and Charlson lists of comorbidities are routinely used for risk adjustment.^{32,33,34} The Elixhauser list is broader than the Charlson list and consists of the following 30 comorbidities:^{32,34} congestive heart failure (CHF), chronic pulmonary disease, hemiplegia or paraplegia, metastatic solid tumour or metastatic cancer, acquired immune deficiency syndrome or human immunodeficiency virus, peripheral vascular disease, cardiac arrhythmias, valvular disease, pulmonary circulation disorders, hypertension (uncomplicated), hypertension (complicated), other neurological disorders, diabetes (uncomplicated), diabetes (complicated), hypothyroidism, renal failure, liver disease, peptic ulcer disease (excluding bleeding), lymphoma, solid tumour without metastasis, rheumatoid arthritis or collagen vascular diseases, coagulopathy, obesity, weight loss, fluid and electrolyte disorders, blood loss anaemia, deficiency anaemia, alcohol abuse, drug abuse, psychoses and depression. Most of the comorbidities on the Charlson list are covered by the Elixhauser list.^{34,33} One notable exception is dementia; however, dementia is defined within one of the frailty variables (see just below).

Work is underway within one of the two STPs that NEHF is part of on identifying frailty conditions. NEHF is considering incorporating these into the future risk stratification model used by the local team. The IAU will use the following list of comorbidities linked to frailty: anxiety or depression; functional dependence; falls and significant fracture; incontinence; mobility problems; pressure ulcers; and cognitive impairment (composite of delirium, dementia and senility), consistent with other IAU analyses.^{30,35}

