The IAU identified a number of ‘overlapping’ in-patient spells (stays) in the SUS data where, for example, a patient spell with one provider did not end before a spell with another provider started. When calculating average length of stay, we did not account for these overlapping spells. Instead, the average length of stay was calculated for each spell, as recorded in the data. Note: For the outcomes emergency bed days and elective bed days, bed days were not double-counted, that is the number of unique days in hospital following either emergency or elective admission were calculated.

Duplicate outpatient appointments were removed. Outpatient appointments relating to mental health services, to the extent these were recorded in the outpatient data, were included.

Index dates and follow-up, page 24

To further limit the size of the dataset of potential controls, only one potential index date per quarter was created for potential patients aged less than 65 years. Only 14% of ICT patients in the study were younger than 65 years.

Baseline variables, page 26

The variables mental ill health and serious mental ill health, as defined on page 32, were included as baseline variables, replacing the mental health definition specified in IPOPAEGP.

Connective tissue disease in the IPOPAEGP was not included as a baseline characteristic, as it overlapped with the Elixhauser definition of rheumatic arthritis. The Elixhauser variable peripheral vascular disorders was not included in error.

Identifying control group, page 28

Due to low numbers of care home residents that were referred to ICTs (<10), matching on type of residence (ie whether a person lived at home, in a nursing or a residential care home) was not done by exact matching.

Matching parameters, page 29

Due to the size of the dataset of potential control patients (approximately 750,000 records), the parameters for the genetic matching algorithm was limited to iterations based on population size 200, maximum generation 100 and number of generations to wait 10.

Statistical analysis, page 30

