Modelling options also included adjusting for only a list of 'core' variables and those variables considered most predictive of the outcome, as the low number of events for some of the outcomes may otherwise have led to over-parametrised models. The most predictive variables were identified by running a lasso regression and where possible included all core variables as a minimum.⁵⁷ Variables considered 'core' were: age; gender (male or not male); IMD quintile; locality; Charlson Index; number of Elixhauser comorbidities; number of frailty comorbidities; history of mental ill health; index date quarter; hospital use in year prior to index date; and emergency admissions, CACS emergency admissions and UCS emergency admissions in the two months prior to index date.

Due to low numbers of care home residents (<10) in both ICT and matched control groups, analyses only adjusted for whether patients lived at home or in a care home (i.e. no differentiation between nursing and residential homes).

Following the analysis, it was found that outpatient appointments included community data from Virgin Care Services that had been uploaded to SUS in error. These appointments were removed from the data and the analysis of outpatient hospital use was redone. Other outcomes were not reanalysed; therefore in the case where these analyses adjusted for outpatient appointments in the year prior to the study, this variable would have contained some community outpatient appointments from Virgin Care Services.

Modelling options did not include multilevel models with locality as a random effect, as five localities were considered too few groups to adequately run such a multilevel model.

Acknowledgements

We are grateful to the North East Hampshire and Farnham CCG team for their support and their review and feedback on an earlier version of this statistical analysis protocol. We are also grateful to [name] and [name] for their peer review comments on an earlier version.

References

- ¹ NEHF CCG. Happy, Healthy, at Home (accessed 29 June 2017). Available from: www.northeasthampshireandfarnhamccg.nhs.uk/about-the-ccg/happy-healthy-at-home
- ² Moran P. Short Stay Emergency Admissions. NEHF CCG, available on request. 2016.

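### Peripheral vascular disease was dropped from the baseline variables by mistake, so the promised balance check on it is missing and no correction is reported

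*Protocol*

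**What the plan says.** In section 2 (Baseline variables), Table 3 includes the "Elixhauser list of comorbidities, identified in the pre-period", and the text below it names the members of that list, among them "peripheral vascular disease, cardiac arrhythmias, valvular disease, pulmonary circulation disorders". The status of the table is set out in the same section: "Potential baseline variables to include in the matching or as covariates in the modelling are listed in Table 3".

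The section on diagnostics is firmer: "Balance will be assessed across all baseline variables listed in the section on Baseline variables". It adds that this applies even to variables left out of the matching algorithm, and it cites 10% as a standardised difference below which imbalance has been regarded as negligible.

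On adjustment, the Baseline variables section says: "Although the IAU expects to adjust for all potential covariates in the regression models". The rest of that sentence allows the set to be cut back by priority when not everything can be adjusted for.

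The addendum of July 2018, under Baseline variables, states: "The Elixhauser variable peripheral vascular disorders was not included in error". Under Statistical analysis, it names the core adjusters, which include the Charlson Index and the "number of Elixhauser comorbidities; number of frailty comorbidities".

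**The concern.** The study is a matched comparison in which referral was by clinical judgement, so its credibility rests on balance in the characteristics that can be observed. The section on internal validity warns that leaving out important predictors can lead to differences being wrongly credited to the intervention. Peripheral vascular disease was observable: comorbidities were to be taken from any diagnosis field of any admission before the index date. Its absence is therefore an avoidable gap, unlike the unobserved confounding that the protocol concedes.

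Two things are at stake. First, a reader who is told that balance was assessed on the planned baseline set would be misled on one item. Second, the mistake may reach a core adjuster: if the Elixhauser count was summed from the same flags, every patient with the condition carries a count one too low.

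**Working it through.** **Step 1: trace the variable.** The document gives no figure to reproduce, so the first check is on the text. I take the condition named in the list and the one named in the addendum to be the same.

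| Use of the variable | What the plan commits to | What the addendum reports |
|---|---|---|
| Balance check | All listed baseline variables, matched on or not | Variable omitted by mistake; no balance figure |
| Matching | A subset, chosen empirically | Could not be chosen |
| Adjustment | Expected for all potential covariates, reducible by priority; addendum adds models with core plus lasso-selected variables | Could not be chosen; not on the core list |
| Charlson Index, Elixhauser count | Core adjusters (addendum) | Not stated whether either contains the condition |

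The Summary makes the addendum the place for recording departures from the plan. Neighbouring entries show what a full entry looks like. Connective tissue disease was dropped because it overlapped with another variable. Exact matching on residence was dropped because of small numbers. For the outpatient data error, the addendum reports a re-analysis of that outcome and states the consequence for the others. The entry for peripheral vascular disorders gives no reason beyond error, no rerun and no consequence.

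**Step 2: scale of a possible bias.** The document gives neither prevalence nor the association with outcome, so both are assumed. Let p1 and p0 be the prevalence in the ICT and control groups, and R the rate ratio between patients with and without the condition.

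- Standardised difference: (p1 − p0) / √{[p1(1 − p1) + p0(1 − p0)] / 2}
- Distortion of the intervention rate ratio when the variable is omitted: [1 + p1(R − 1)] / [1 + p0(R − 1)]

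Worked example with p1 = 15%, p0 = 10%:

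- Standardised difference = 0.05 / √[(0.1275 + 0.0900) / 2] = 0.152, or 15.2%.
- Distortion at R = 1.3: 1.045 / 1.030 = 1.015. At R = 1.5: 1.075 / 1.050 = 1.024.

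| p1 v p0 | Standardised difference | R = 1.2 | R = 1.5 | R = 2.0 |
|---|---|---|---|---|
| 12% v 10% | 6.4% | 1.0039 | 1.0095 | 1.0182 |
| 7.4% v 5% | 10% | 1.0048 | 1.0118 | 1.0230 |
| 13.2% v 10% | 10% | 1.0063 | 1.0152 | 1.0291 |
| 18.7% v 15% | 10% | 1.0073 | 1.0174 | 1.0325 |
| 15% v 10% | 15.2% | 1.0098 | 1.0238 | 1.0455 |
| 10% v 5% | 19.1% | 1.0099 | 1.0244 | 1.0476 |
| 20% v 10% | 28.3% | 1.0196 | 1.0476 | 1.0909 |

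If prevalence is equal, the factor is 1. If controls have more of the condition, the factor is the reciprocal, so the direction is also unknown. All entries ignore what correlated covariates absorb.

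**Step 3: compare with sampling error.** The protocol expects about 900 ICT patients, matched 1:1. With an assumed mean of m admissions per patient in each group, the Poisson standard error of the log rate ratio is √[2 / (900m)]. For m = 0.5 this is 0.0667, and exp(1.96 × 0.0667) = 1.14. For m = 2 it is 0.0333, and exp(1.96 × 0.0333) = 1.07. The 95% limits are therefore roughly 7% to 14% from the estimate, and wider with over-dispersion. Most entries in the table lie well inside that.

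**The case against.** The strongest reply is that the authors have disclosed the omission in the place set aside for it, and that a difference between plan and addendum is what an addendum exists to record. That is fair as far as it goes. But the entry admits a mistake rather than a decision, and disclosure does not supply the missing balance figure.

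A second reply is that the condition may already be partly captured. The Charlson Index is a core adjuster, and the protocol says that most Charlson conditions are covered by the Elixhauser list and gives dementia as a notable exception. Age, prior hospital use and the frailty count are also core adjusters. This stands as a reason to expect little residual bias, but the document does not say what either summary score contains.

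A reader might infer several stronger things that the document does not support:

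- **That adjustment for the condition was promised and the promise broken.** Table 3 lists potential variables, matching was to use a subset, full adjustment was only expected, and the addendum allows lasso-selected models in which this condition is not core. Only the balance check was unconditional.
- **That the groups are unbalanced, or the estimates confounded, on this condition.** The document reports no balance result, and the warning about omitted covariates concerns important predictors. Nothing shows that this one matters once the others are adjusted for.
- **That nobody has looked.** The lack of a repair is read from the addendum's silence. Balance tables and tested models belong to the report and technical appendix, which are not at hand.
- **That the match must be redone and the main estimates replaced.** The likely size does not justify this, and changing the main estimates after results are known has its own drawbacks.

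**Conclusion.** The point holds in a limited form. A listed comorbidity was left out by mistake, the promised balance check on all listed baseline variables was therefore not met for it, and the addendum reports no correction. It also had no opportunity to enter the matching or the models. Whether the Elixhauser count is short by one for affected patients depends on how it was built, which is not stated; if so, it is short in both groups alike.

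The size of any bias is unknown. At a standardised difference of 10%, with R from 1.2 to 2.0, the rate ratio would be distorted by about 0.5% to 3%. With the larger assumed imbalances the range is about 1% to 9%, the top needing both a twofold prevalence difference and a doubled event rate. A few per cent at most is the reasonable expectation, before absorption by correlated covariates. That is modest beside the sampling error and the unobserved confounding that the protocol acknowledges. The repair is nevertheless worth making, because the data are already held.

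**What to change.** 1. Derive the peripheral vascular disease flag from the pre-period diagnosis fields.
2. Report its prevalence in each matched group and its standardised difference, as an added row in the balance table.
3. State in the addendum whether the Charlson Index and the Elixhauser count include the condition. If the count does not, correct it.
4. Rerun the adjusted models with the flag and the corrected count, and show the results beside the existing adjusted estimates as a sensitivity analysis.
5. Do not rematch. If the standardised difference exceeds 10%, state this as a limitation and give weight to the adjusted rerun.

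The cost is one code list, one balance row, a sentence or two in the addendum, and a rerun of existing models for the twelve listed outcomes (five primary, seven secondary). The matching search over roughly 750,000 candidate control records is not repeated.
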